2.5. Secondary Endpoints

Secondary endpoints in this study are related to clinical activity. These include the following:

[figure not shown]
- Objective response rate (ORR), with overall response defined as best response of complete response (CR), CR with incomplete marrow recovery (CRi), partial response (PR), or PR with lymphocytosis (PRwL) according to the 2008 International Workshop on Chronic Lymphocytic Leukemia Response Criteria (IWCLL) with modifications for treatment-related lymphocytosis.
- Duration of response (DoR), defined as time from first documentation of response to first documentation of progressive disease (PD) per 2008 IWCLL, first new therapy including allogeneic transplantation, or death due to any cause.
- Progression free survival (PFS), defined as time from first dose of study treatment to the first documentation of PD, first new therapy excluding allogeneic transplantation, or death due to any cause.
- Overall survival (OS), defined as time from first dose of study treatment to death due to any cause.
- Disease control rate (DCR) defined as the percentage of patients who have achieved CR, CRi, PR, PRwL and stable disease (SD). Duration of stable disease with stable disease defined as at least 6 months from the start of MS-553 monotherapy to first

documentation of progressive disease (PD) in relapsed and refractory CLL/SLL patients.

• Pharmacokinetics of MS-553 monotherapy, as well as the small molecule agents used in combination, acalabrutinib, or venetoclax.

[figure not shown]

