3.2. Treatment Duration

Patients will be treated in 28-day cycles. Patients on this study may continue receiving study drug provided they continue to tolerate the drug, have no evidence of progression, do not meet any of the criteria for discontinuation, and the patient's participation in the study has not ended. The anticipated median treatment duration is unknown. Patients who have discontinued treatment for progressive disease and/or who have started another anticancer therapy or an investigational

product, will be followed for survival every 24 weeks (± 7 days) for up to 3 years (follow up can include clinic visit, chart review or telephone contact). Patients who discontinue treatment for reasons other than progressive disease, use of other anticancer therapy or an investigational product, death, or withdrawal of consent will have response assessments every 12 weeks (± 7 days) until progressive disease occurs. Thereafter they will be followed for survival every 24 weeks (± 7 days) for up to 3 years. All patients will discontinue survival follow-up upon completion of 3 years of survival follow-up, withdrawal of consent, death, or study closure, whichever is the earliest. The Sponsor reserves the right to discontinue the study for clinical or administrative reasons at any time.

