3.7. Response Assessment

Response data will be collected at screening and on day 1 of every cycle beginning with the first treatment visit and ending at the end of treatment visit, which should occur 30 (+ 7 days) after the last dose of study drug, if the condition of the patient permits, or up to the start of other anti-cancer therapy or investigational drug product(s), whichever is sooner. Patients who discontinue treatment for reasons other than progressive disease, use of other anticancer therapy or an investigational drug product, death, or withdrawal of consent will undergo response assessments every 12 weeks (± 7 days) until progressive disease occurs.

Response data consists of a combination of interviews, physical exams, labs, and scans. Not all labs and scans will be obtained at each time point. See Section 6.2 and Appendix 1 for complete details.

4. **PATIENT POPULATION**

CLL is most commonly a disease of the elderly, with a median age at diagnosis of 71, but disease has been witnessed in adults of all ages. This study is targeted at CLL adults of any age who meet the inclusion criteria for the cohort to which the patient is enrolled.

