4.1. Inclusion Criteria

To be eligible for inclusion in the **dose escalation cohorts or expansion cohorts** in this study, patients must meet all of the following criteria:

- 1. Age 18 years or older.
- 2. Diagnosis of CLL or SLL:
 - a. History of histologically documented CLL or SLL that meets IWCLL diagnostic criteria according to the 2008 guidelines, and
 - b. Indication for treatment as defined by the 2008 IWCLL guidelines, or the need for disease reduction prior to allogeneic transplantation.
- 3. Cohort specific inclusion requirements:

Cohort A1 (MS-553 monotherapy)

Relapsed after, or is refractory to, progressing after at least two prior lines of therapies with the following exceptions:

- a. Patients with a 17p deletion who have already received venetoclax; or
- b. Patients who have *TP53* mutation (prior therapy is not required) which shall be confirmed at screening for enrollment.

- c. Patients with clinical and/ or molecular (e.g., BTK and/or PLCG2 mutation) resistance after achieving initial response to a BTK inhibitor.
 - For patients without clinical resistance, molecular resistance (i.e., BTK and/or PLCG2 mutation) shall be confirmed at screening for enrollment.

Cohort A2 (MS-553 monotherapy)

Relapsed/refractory CLL/SLL patients who have:

a. Failed at least two prior lines of therapies, or

- b. Developed clinical and/or molecular (i.e., BTK and/or PLCG2 mutation) resistance after achieving an initial response to a BTK inhibitor
 - For patients without clinical resistance, molecular resistance (i.e., BTK and/or PLCG2 mutation) shall be confirmed at screening for enrollment.

Cohort A3 (MS-553 monotherapy) See Inclusion Criterion #4 below

Cohort B1, B2 (MS-553 in combination with acalabrutinib)

Treatment experienced patients with no more than two prior lines of therapies, who

- a. Are naïve to prior BTK inhibitor treatments, and
- b. Are eligible for single agent BTK inhibitor

Cohort B3 (MS-553 in combination with acalabrutinib)

Treatment experienced patients with no more than two prior lines of therapies, who

- a. Are naïve to prior BTK inhibitor treatments, and
- b. Are eligible for single agent BTK inhibitor, and
- c. Have 17p deletion or TP53 mutation which shall be confirmed screening for enrollment.

at

Cohort C1, C2 (triplet regimen of MS-553 + rituximab + venetoclax)

Treatment experienced patients receiving no more than 2 prior lines of treatment regimens, who

- a. Are naïve to prior Bcl-2 inhibitor treatments, and

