Secondary efficacy endpoints in all cohorts include overall response rate (ORR), duration of response (DoR), disease control rate (DCR), PFS, and OS. For patients achieving a response, the response duration will be measured from the time at which criteria for CR, PR, or PR with lymphocytosis is first assessed until the date at which recurrent or progressive disease or death due to disease is documented. Stable disease, a component of DCR, is defined as at least 6 months from the start of MS-553 monotherapy until to first documentation of progressive disease (PD) in relapsed and refractory CLL/SLL patients. Progression free survival will be measured as the time from the first dose of the study drug until disease progression or death from any cause. Overall survival will be measured as the time from the study drug until death due to any cause. For the secondary efficacy endpoints of response duration, PFS, and OS, patients who have not progressed or died at the time of last known status will be censored at that time; for response duration and PFS, patients may also be censored at the time

of subsequent treatment if a prior progression is not documented. See Section 8, Statistics, for more complete details on censoring.

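### PFS is defined to run on through allogeneic transplantation, but progression after transplant is not reliably ascertained and the censoring rules conflict

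*Combined protocol and SAP*

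**What the plan says.** **Endpoint definitions.** Section 2.5, with the same definition in the Synopsis, ends PFS at "first documentation of PD, first new therapy excluding allogeneic transplantation, or death due to any cause". Duration of response, defined just before it, ends at "first new therapy including allogeneic transplantation, or death due to any cause". Transplantation thus ends response duration but not PFS, and both phrases treat it as a kind of new therapy.

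**Efficacy section.** Section 6.2.2 words PFS differently: "Progression free survival will be measured as the time from the first dose of the study drug until disease progression or death" from any cause. New therapy is not an event there, and transplant is not mentioned. On censoring it says "patients who have not progressed or died at the time of last known status will be censored at that time", and then "for response duration and PFS, patients may also be censored at the time" of a later treatment when no earlier progression is on record. It sends the reader to Section 8 for the details. The readable text of Section 8 describes an analysis of ORR (Section 8.8) and gives no censoring rule for any time-to-event endpoint.

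**Follow-up.** Section 3.2 places one group on survival follow-up every 24 weeks for up to 3 years, by visit, chart review or telephone: "Patients who have discontinued treatment for progressive disease and/or who have started another anticancer therapy or an investigational" product. Response assessments every 12 weeks until progression go to a different group, described in Section 3.7 as "Patients who discontinue treatment for reasons other than progressive disease, use of other anticancer therapy or an investigational drug product, death" or withdrawal of consent. The Synopsis (Cohorts A, B and C) and footnote b of Appendices 1A, 1B and 1C repeat the split. The footnotes ask for no more than a chart review or a call. None of these places makes an exception for transplant.

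**Entry.** Criterion 2b in Section 4.1 accepts "the need for disease reduction prior to allogeneic transplantation" as an alternative to a standard treatment indication.

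**The concern.** An endpoint that keeps its clock running after an intervention needs progression to be looked for after that intervention. Here the definition and the follow-up schedule appear to have been written separately. A patient who stops MS-553 without progression and goes to transplant stays at risk for PFS under Section 2.5. On the natural reading of Section 3.2, the same patient has no further scheduled response assessment. Transplant is a foreseen path, since some patients may enter for that purpose.

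At stake is whether reported PFS for these patients is progression-free time or merely time alive. The choice of handling is also left open in an open-label study, where it could be made after the data are known.

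**Working it through.** The plan states no PFS figure (no expected median, event count, power or alpha), so there is nothing to reproduce. The check is a comparison of the text, followed by an illustration of direction.

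**1. The two PFS rules side by side**

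| Situation | Section 2.5 and Synopsis | Section 6.2.2 |
|---|---|---|
| Progression or death | Event | Event |
| New therapy other than transplant, no progression | Event | Not an event; may be censored |
| Transplant, no progression | Clock runs on | Not mentioned; may be censored if it is a subsequent treatment |
| No event | Not stated | Censored at last known status |

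The rules agree only in the first row.

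**2. Follow-up of a patient transplanted without progression**

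- Reading A: transplant is other anticancer therapy. Follow-up is survival contact only. Section 2.5 favours this reading, because it calls transplant a form of new therapy.
- Reading B: transplant is not other anticancer therapy. The 12-weekly response assessments continue until progression.

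No section says which applies.

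**3. Unassessed time under Reading A**

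Three years of survival follow-up is 3 × 52 = 156 weeks. At 24-week intervals that is 156 / 24 = 6.5, so about six contacts, none requiring a response assessment. On the 12-week schedule the same span would hold 156 / 12 = 13 assessments for a patient who stays progression-free. If last known status means vital status, a surviving patient can be credited with up to about 156 weeks of PFS with no scheduled disease assessment behind it.

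**4. Direction of bias (illustration only)**

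Every input is an assumption; none is in the documents. There were 200,000 simulated patients per scenario, with exponential times. Median time to progression was 12 months without transplant. A share of 5, 10, 20 or 30% was scheduled for transplant at months 3 to 9, of whom 3.5 to 21.4% of all patients reached it before progression. Median time from transplant to progression was 6, 12 or 24 months. Death followed that progression by a median of 18 months, and the cut-off was 42 months. Kaplan-Meier PFS at 24 months over the 12 scenarios:

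| Handling of transplanted patients | 24-month PFS | Difference from (a) |
|---|---|---|
| (a) Progression after transplant observed | 20.1 to 30.1% | reference |
| (b) Progression unseen, only death counted | 26.2 to 36.2% | +1.0 to +11.9 points |
| (c) Censored at transplant | 24.9 to 25.0% | −5.2 to +4.9 points |
| (d) Transplant counted as an event | 17.4 to 23.8% | −12.7 to −0.5 points |

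Examples at the 30% scheduled share: with a 6-month post-transplant median, (b) − (a) = 32.0 − 20.1 = +11.9 and (c) − (a) = 25.0 − 20.1 = +4.9. With a 24-month median, (c) − (a) = 24.9 − 30.1 = −5.2 and (d) − (a) = 17.4 − 30.1 = −12.7.

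Under (b) the bias is upward in every scenario. Under (c) it has no fixed direction. The plan permits both.

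**The case against.** A reader might infer that progression after transplant cannot be seen and that PFS is therefore overstated by a calculable amount. For example, transplant at month 6, relapse at month 18 and death at month 30 would give 30 / 18 = 1.67, or 67% too long. The documents do not support that, for these reasons:

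- Section 6.2.2 allows censoring at subsequent treatment. If transplant counts as one, that patient could be censored at month 6, and unseen relapse would not lengthen PFS directly.
- Under Section 2.5 only transplant is excluded. Any other new therapy given for the relapse would still end PFS.
- A chart review is an allowed contact and could document progression.
- No section classes transplant as other anticancer therapy for follow-up. Under Reading B the wanted assessments are already scheduled.
- The documents give no transplant rate, relapse time or survival time, and do not say that transplanted patients are selected responders.

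All of this stands against a fixed, upward, quantified bias. It does not settle the matter. An optional censoring rule is not a rule, and this one contradicts Section 2.5. A progression that a chart happens to show is not the same as one that is looked for. An ambiguity that sites can resolve in two ways still needs a clause. It is also fair that PFS is secondary and descriptive: Section 8.4 says no hypothesis is tested, and no dose or continuation rule uses PFS.

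**Conclusion.** The point holds in this form. PFS is defined to run through allogeneic transplantation, the follow-up rules do not secure progression assessment afterwards, and Sections 2.5 and 6.2.2 give conflicting rules that the readable Section 8 does not resolve. PFS for transplanted patients can be overstated if three conditions meet: transplant is treated as other anticancer therapy, patients stay at risk after it, and censoring falls at last known survival status. If they are instead censored at transplant, the bias can go either way.

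The number of patients affected is unknown and could be nil, so no size can be given; the simulated figures show direction only. The change should be made because the stated rules, followed as written, can yield a wrong PFS, and because progression data not collected on schedule may be unrecoverable later. It does not touch the primary safety endpoints.

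**What to change.** 1. State one PFS rule and use it in the Synopsis, Section 2.5 and Section 6.2.2. Say whether new therapy is an event or a censoring point, and how transplant is handled. Put the full censoring rule in Section 8, where Section 6.2.2 already points.
2. Censor PFS at the last adequate disease assessment, not at last known survival status.
3. If PFS is to run through transplant, say that transplant without prior progression does not count as other anticancer or CLL/SLL therapy, so that the existing 12-weekly response assessments continue to progression. The clause belongs in all eight places: the Synopsis follow-up text for Cohorts A, B and C, Section 3.2, Section 3.7, and footnote b of Appendices 1A, 1B and 1C. Where a patient has no assessment after transplant, censor at the last one before it.
4. Add a sensitivity analysis that counts transplant as a PFS event.

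The cost is one repeated clause and one censoring rule in the text, 12-weekly assessments for the few patients transplanted, and possibly a slightly shorter reported PFS.

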2.6. Exploratory Endpoints

Cohort A:

Cohort B:

Samples: For Cohort B, the samples being collected in this study for the measurement of exploratory endpoints are:

Cohort C:

Samples: For Cohort C, the samples being collected in this study **for the measurement of exploratory endpoints are**:

_	

3. INVESTIGATIONAL PLAN

3.1. Overview of Study Design

This is a Phase I/II multi-center, open-label study of single agent MS-553, as well as MS-553 in combination with acalabrutinib or venetoclax and rituximab in treatment experienced CLL/SLL patients.

The study will consist of 3 cohorts. Cohort A will evaluate MS-553 monotherapy, Cohort B will evaluate MS-553 in combination with acalabrutinib, and Cohort C will evaluate MS-553 in combination with venetoclax and rituximab. A schema of the three cohorts is shown in Figure 1 in Section 3.1.4.

3.1.1. Cohort A: MS-553 Monotherapy

The first part of the study, the dose escalation portion (Cohort A1), will determine the safety of MS-553 and the MTD or initial RP2D. After the initial RP2D is identified, an expansion cohort (Cohort A2) will be started at the MTD or initial RP2D, enrolling approximately 25 patients with relapsed/refractory CLL/SLL who (a) have failed at least two prior lines of therapies, or (b) have either acquired clinical and/or molecular resistance to a BTK inhibitor (i.e., BTK and/or PLCG2 mutation) after achieving initial response to a BTK inhibitor. In addition, an optional expansion cohort (Cohort A3) of approximately 25 patients with aggressive lymphoma, including Richter's transformation, DLBCL and MCL will be enrolled. At least 15 patients in Cohort A3 shall be MCL patients.

additional patients will be enrolled in Cohort A2 to further testing two dose levels before a final RP2D can be declared.

The two dose schedules designated as dose schedule 1 (DS1) and dose schedule 2 (DS2) are as follows:

	MS-553 Oral Daily Dose
Week 1	150 mg BID
Week 2	200 mg BID
Week 3 and beyond	250 mg BID

Dose Schedule 1 (DS1)

Dose Schedule 2 (DS2)

	MS-553 Oral Daily Dose
Cycle 1 and beyond	225 mg BID

Twenty of the 40 additional patients will be treated with DS1 and the other 20 patients with DS2. The patients will be allocated to either DS1 or DS2 in alternating fashion, according to the sequence of their enrollment. For example, the first enrolled patient will be allocated to DS1, the second patient to DS2, the third patient to DS1, the fourth to DS2, and so on.

The optional expansion cohort (Cohort A3) will be closed to accommodate the new dose testing plan.

3.1.2. Cohort B: MS-553 in combination with acalabrutinib

As soon as the MTD or initial RP2D is declared for MS-553 monotherapy in Cohort A1, MTD or initial RP2D of MS-553 in combination with acalabrutinib will be evaluated at an MS-553 starting dose of 150 mg BID (Cohort B1) in treatment experienced CLL/SLL patients who are BTK inhibitor naïve, eligible for standard of care treatment with a BTK inhibitor as a single agent and who have had no more than 2 previous lines of treament regimens. The number of patients in the dose escalation will range from 3 to approximately 12 patients. Once the MTD or initial RP2D is known for the combination (Cohort B1), two expansion cohorts (B2 and B3) will be started in parallel to further evaluate the safety of the combination regimens, as well as to assess early evidence of anti-tumor activity.

One of the expansion cohorts (Cohort B2) will evaluate MS-553 in combination with acalabrutinib in treatment experienced CLL/SLL patients who are BTK inhibitor naïve, are eligible for treatment with a BTK inhibitor as a single agent, and who have had no more than 2 previous lines of treatment regimens. Approximately 20 patients will be enrolled in Cohort B2 to further confirm the safety of the combination and assess early evidence of anti-tumor activity.

The other expansion cohort (Cohort B3) will evaluate MS-553 in combination with acalabrutinib in treatment experienced CLL/SLL patients who have received no more than 2 prior lines of therapy and have TP53 abnormalities (including 17p deletion and P53 mutations). Once this cohort is open, all patients with TP53 abnormalities who are also naïve to BTK inhibitors will be preferentially enrolled in Cohort B3, rather than Expansion Cohorts B2. Approximately 10 treatment experienced CLL/SLL patients eligible for standard of care acalabrutinib will be enrolled in Cohort B3 to further confirm the safety of the combination and assess early evidence of anti-tumor activity.

3.1.3. Cohort C: MS-553 in combination with venetoclax and rituximab

As soon as the MTD or initial RP2D is declared for MS-553 monotherapy in Cohort A1, MS-553 will be evaluated in combination with venetoclax and rituximab at the starting dose of 150 mg BID in treatment experienced CLL/SLL patients who are eligible for standard of care venetoclax and rituximab, naïve to prior Bcl-2 inhibitor treatment, and have had no more than 2 prior lines of treatment regimens. The number of patients in dose escalation will range from 3 to approximately 12 patients per dose group.

Once the MTD or initial RP2D is known for the combination (Cohort C1), one expansion cohort will be initiated to further evaluate the safety of the combination regimen, as well as to assess early evidence of anti-tumor activity. This cohort (Cohort C2) will enroll treatment experienced CLL/SLL patients who are eligible for standard of care venetoclax and rituximab, naïve to prior Bcl-2 inhibitor treatment and have had no more than 2 previous lines of treatment regimens. Approximately 20 patients will be enrolled to further confirm the safety of the combination and assess early evidence of anti-tumor activity.

3.1.4. Study Design Schematic

[figure not shown]

Figure 1: Study Schema

Figure 1: Cohort schema including dose escalation for monotherapy and each of the combinations as well as subsequent expansion cohorts.

3.2. Treatment Duration

Patients will be treated in 28-day cycles. Patients on this study may continue receiving study drug provided they continue to tolerate the drug, have no evidence of progression, do not meet any of the criteria for discontinuation, and the patient's participation in the study has not ended. The anticipated median treatment duration is unknown. Patients who have discontinued treatment for progressive disease and/or who have started another anticancer therapy or an investigational

product, will be followed for survival every 24 weeks (± 7 days) for up to 3 years (follow up can include clinic visit, chart review or telephone contact). Patients who discontinue treatment for reasons other than progressive disease, use of other anticancer therapy or an investigational product, death, or withdrawal of consent will have response assessments every 12 weeks (± 7 days) until progressive disease occurs. Thereafter they will be followed for survival every 24 weeks (± 7 days) for up to 3 years. All patients will discontinue survival follow-up upon completion of 3 years of survival follow-up, withdrawal of consent, death, or study closure, whichever is the earliest. The Sponsor reserves the right to discontinue the study for clinical or administrative reasons at any time.

